### **3.4. Protocol deviations**

The serious protocol deviations that required patient exclusion from the final analysis are: missed two or more scheduled DUS; missed the final scheduled DUS before discharge; autopsy rejected; inability to assess compliance with IPC (no information in the Compliance sheet); gross inconsistencies between source documentation and an CRF; violations of the procedure for obtaining informed consent; failure to follow the procedures of the trial protocol; the inability to collect all the data used in evaluating the final goals of the study (for example, the lack of records in the source documentation necessary to verify the inclusion/exclusion criteria, safety, and efficiency criteria); any other protocol deviations considered as significant.

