## 8. Statistical analysis plan and sample size calculation

**Statistical analysis plan.** The primary statistical analysis is designed as intention-to-treat with the use of two-tailed Fisher's exact test to compare the primary endpoint between two groups. The primary endpoint will be reported as an absolute number, percentage, and relative risk with 95% CI. Secondary statistical analysis of the primary endpoint will be made using an unadjusted Cox proportional-hazards model. The data will be censored on the time of VTE registration, or death, or discharge from the hospital and reported as a hazard ration with 95% CI. Kaplan-Meier curves will be used to compare time-to-event distribution. Cox proportional-hazards models adjusted for the clinical center, surgery profile, type of surgery, emergency of surgery, type of anesthesia, surgical radicalism, malignant disorder, Caprini score, and time to start LMWH injections will be used.

A similar analysis for the per-protocol population, but that excluded patients with gross violations of the protocol and premature discontinuation of at least one component of combined prophylaxis (ECS, IPC or LMWH), will be performed for the primary endpoint.

Secondary endpoints will be analyzed with two-tailed Fisher's exact test and will be represented as an absolute number, percentage, and relative risk with 95% CI.

Cox proportional-hazards models will be used for the prespecified subgroup analysis for the following subgroups: surgical profile; type of surgery; the urgency of surgery; the radicalism of surgery; type of anesthesia; malignant or benign disorder; preoperative, postoperative, or delayed start of LMWH injections; and pre-operative or post-operative IPC application.

Sensitivity analysis will address to the per-protocol analysis, compliance with IPC (restricted for 90% and more), duration of follow-up (restricted to 7 days and more), and the number of postoperative DUS (restricted with two and more).

Missing data on the primary endpoint are not anticipated in the inpatient settings, so no analysis for missing data being planned.

Adjusting for multiple comparisons and imputation for missing values will not be performed. The 95% confidence intervals will be not adjusted for multiplicity, and therefore, inferences drawn from these intervals might be not reproducible. The interim analysis is not planned.

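### The primary analysis is declared intention-to-treat, but sections 3.4 and 4.2 remove randomised patients from the analysis without limiting this to the per-protocol set

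*Combined protocol and SAP*

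**What the plan says.** Three places in the combined protocol and SAP say who is analysed.

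- Section 8: "The primary statistical analysis is designed as intention-to-treat", using a two-tailed Fisher's exact test on the primary endpoint. It then adds "A similar analysis for the per-protocol population, but that excluded patients with gross violations of the protocol", which also drops patients who stopped a component of prophylaxis early. Among the sensitivity analyses it lists IPC compliance of at least 90% "and the number of postoperative DUS (restricted with two and more").
- Section 3.4: "The serious protocol deviations that required patient exclusion from the final analysis are: missed two or more scheduled DUS". The list goes on with "missed the final scheduled DUS before discharge; autopsy rejected", "inability to assess compliance with IPC (no information in the Compliance sheet"), failure to follow trial procedures, consent violations, missing records and "any other protocol deviations considered as significant".
- Section 4.2: patients who have not received enoxaparin after 5 days are withdrawn from the analysis.

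On missing outcomes, section 8 says: "Missing data on the primary endpoint are not anticipated in the inpatient settings, so no analysis for missing data being planned". It also rules out imputation. The sample size paragraph nevertheless adds 10% for withdrawals that include protocol deviations and incomplete data.

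**The concern.** An intention-to-treat comparison keeps every randomised patient in the allocated arm. Sections 3.4 and 4.2 remove randomised patients, and neither names the per-protocol set. Section 8 does not refer back to them, uses a different term (gross violations, where 3.4 speaks of serious deviations), and does not define the intention-to-treat set. If 3.4 and 4.2 are applied as written, the primary test is not intention-to-treat.

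The grounds themselves make this more than a matter of labels:

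- Most arise after randomisation, such as missed scans or procedures not followed. Consent violations and missing eligibility records need not.
- The blank compliance sheet can occur only in the IPC arm, because section 5.6 records compliance for IPC alone.
- The final catch-all names no decision-maker, in a trial where allocation is known.
- The refused-autopsy ground removes a patient for lack of a test that the primary endpoint, based on ultrasound (section 3.5), does not use. Read literally, it would also drop a known death from the postoperative mortality endpoint.
- The 5-day rule in 4.2 repeats an exclusion criterion in 3.2 and applies to both arms. But screening ends at the latest 12 h after surgery, so it can be applied only days after enrolment.

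At stake is whether the randomised comparison is preserved, and whether the choice of population could be made after outcomes are known.

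**Working it through.** **Which reading does the text support?**

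For a wider primary set: section 8 has a separate per-protocol analysis and treats scan count and compliance as sensitivity restrictions, so patients with fewer scans seem to stay in the main analysis.

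For exclusion from the primary test: the wording of 3.4 and 4.2 is unrestricted, and the 10% allowance fits removing such patients, though it does not prove it.

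No cross-reference settles the matter.

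**The plan's own sample size**

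Inputs (section 8): control risk 30%, relative reduction 60%, so IPC risk 0.30 × (1 − 0.60) = 12%; two-sided alpha 0.05; power 80%. The two-proportion formula with continuity correction gives 90 per arm, and exact Fisher power there is 0.812. Then 180 / (1 − 0.10) = 200, and doubling gives 400, or 200 per arm (implied; the total is not stated). The figures reproduce. The allowance amounts to 0.10 × 400 = 40 patients.

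Power is not the problem: at 30% v 12%, Fisher power is 0.993 with 200 per arm and 0.987 with 180.

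**Illustration 1: no true effect**

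Assumptions: 30% risk in both arms, 200 randomised per arm, a fraction f of the IPC arm excluded, and risk r among those excluded. The documents give neither f nor r.

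Retained IPC risk = (0.30 − f × r) / (1 − f). For f = 0.10 and r = 0.70 this is (0.30 − 0.07) / 0.90 = 0.256, an apparent relative risk of 0.256 / 0.30 = 0.85. Two-sided Fisher rejection rates come from full binomial enumeration:

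| Excluded, IPC only | r = 30% | r = 50% | r = 70% | r = 100% |
|---|---|---|---|---|
| 2% (196 v 200) | 4.40% | 4.44% | 4.65% | 5.27% |
| 5% (190 v 200) | 4.39% | 4.98% | 6.74% | 11.81% |
| 10% (180 v 200) | 4.40% | 6.83% | 14.78% | 38.38% |

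- With all patients analysed (200 v 200) the rate is 3.91%. The step from 3.9% to 4.4% in the r = 30% column is not bias: the retained risk there is exactly 30%, and the change comes from the discreteness of Fisher's test with unequal arms.
- In the 10% row the apparent relative risks are 1.00, 0.93, 0.85 and 0.74.
- The direction can reverse. With f = 0.10 and r = 0, the retained risk is 0.30 / 0.90 = 0.333, the apparent relative risk is 1.11 and the rejection rate is 9.78%.
- With 10% excluded from both arms at equal r (180 v 180), the rates are 3.74% to 3.79%, so there is no inflation.

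**Illustration 2: the planned effect**

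Assume 10% excluded per arm. Retained events: 0.12 × 180 = 21.6, taken as 22, v 0.30 × 180 = 54. Fisher p = 0.00005. Now add back the 20 excluded patients per arm:

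| Events in excluded controls | Events in excluded IPC | Totals, IPC v control | p |
|---|---|---|---|
| 0/20 | 14/20 | 36/200 v 54/200 | 0.041 |
| 0/20 | 15/20 | 37/200 v 54/200 | 0.056 |
| 0/20 | 20/20 | 42/200 v 54/200 | 0.198 |
| 3/20 | 18/20 | 40/200 v 57/200 | 0.062 |
| 6/20 | 19/20 | 41/200 v 60/200 | 0.038 |
| 6/20 | 20/20 | 42/200 v 60/200 | 0.051 |
| 10/20 | 20/20 | 42/200 v 64/200 | 0.017 |

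Significance is lost only when the excluded IPC patients had far more events than the excluded controls.

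**The case against.** The strongest reply is that this is an unassigned rule rather than a true contradiction. Section 8 is the analysis plan, it names intention-to-treat as primary, and its gross violations are most naturally the serious deviations of 3.4. The scan-count and compliance restrictions point the same way. This is a fair guess at what was meant, but the reader has to supply the link: the terms differ, and the exclusions in 3.4 and 4.2 carry no qualifier. Even on this reading, nothing says how a patient without a final scan enters the Fisher test.

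Second, the large error rates need unlikely inputs. The 38.4% requires 20 IPC patients excluded, all with thrombosis, and no controls excluded. Only the blank-sheet ground is confined to the IPC arm, section 5.6 schedules five checks a day, and nothing links a blank sheet to thrombosis. This stands: the figures show what could happen, not what is expected.

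Third, some of the context is reassuring. Efficacy outcomes have a blinded assessor, which limits bias in reading scans but does not govern who is excluded. Autopsy serves to verify the absence of DVT and PE (section 5.4), so it bears on fatal PE and total VTE events. That does not justify removing a patient from the ultrasound-based primary comparison or from mortality.

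**Conclusion.** The concern holds, with high confidence, and should be fixed before analysis. Read as written, sections 3.4 and 4.2 conflict with the intention-to-treat statement in section 8, and the documents do not resolve it. The severity rests on the population of the primary test being open to choice, not on demonstrated bias.

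The size and direction of any bias are unknown. Under the assumptions above, one-arm exclusion of 2% hardly matters (at most 5.3% false positives), 5% could matter if the excluded patients were at much higher risk (up to 11.8%), and balanced exclusion at equal risk does no harm. An effect of the planned size would usually survive either choice of population.

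**What to change.** - Section 8: define the primary set, for example *the ITT set is all randomised patients, analysed as allocated*. State how a patient without a final scan or autopsy counts in the Fisher test, for example on all inpatient scans done.
- Sections 3.4 and 4.2: say that these exclusions apply to the per-protocol set only. Use one term for serious deviations and gross violations. Handle consent violations separately.
- Mortality: count every known death, with or without autopsy.
- Missing outcomes: replace the statement that none are anticipated with a prespecified sensitivity analysis, such as best and worst case.
- Reporting: give exclusions by arm and reason.

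The first two items are essential, and the rest make the result checkable. The cost is wording in three sections and one added analysis. No extra patients or visits are needed, and no treatment rule changes.

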### 3. Design

A two-center, prospective, randomized (with independent allocation), open-label clinical trial with a blinded assessor for efficacy outcomes, enrolling patients at extremely high risk for postoperative VTE (Caprini score of 11 and more). The patients should be randomly allocated into two groups (experimental [IPC] group and control group) according to the VTE prophylaxis they received. Both groups will receive anti-embolic stockings and injections of LMWH, and patients in the IPC group additionally will receive IPC. The total duration of prophylaxis should amount of 1 month, and patients will be followed-up for 6 months with regular clinical examination and duplex ultrasound scans. Figure 1 represents the global design of the study.

[figure not shown]

**Figure 1.** The global design of the study.

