### 5.6. Compliance measure

No specific compliance measures are designed for the use of ECS and LMWH injections. The compliance with the IPC device will be measured as follows. Every day, the investigator (weekdays) or surgeon on duty (weekends and holidays) should visit a patient five times and check that, if the subject is confined to bed, the sleeves are applied to his legs and that the pump is functioning. The results of such visits should be registered in a specifically designed compliance sheet (Fig. 4). The compliance will be calculated as a proportion of all marks testified that IPC was applied to the total number of visits that found patient in the bed.

		Visit 1	Visit 2	Visit 3	Visit 4	Visit 5	Compliance
Day X	Patient is in bed	√	√	√	√	√	100%
	IPC is turned on	√	√	√	√	√	
Day Y	Patient is in bed	√	-	-	-	√	100%
	IPC is turned on	√	-	-	-	√	
Day Z	Patient is in bed	√	√	√	√	√	40%
	IPC is turned on	√				√	

**Figure 4.** An example compliance sheet, which assessed compliance with IPC. The right column represents the result of the calculations.

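### A missing IPC compliance sheet is a ground for exclusion from the final analysis, and this rule can remove patients from the IPC arm only

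*Combined protocol and SAP*

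**What the plan says.** Section 3.4 (Protocol deviations) opens its list with "The serious protocol deviations that required patient exclusion from the final analysis are", and one item is "inability to assess compliance with IPC (no information in the Compliance sheet". It does not say which analysis population is meant.

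Section 3 (Design) sets the arms: "Both groups will receive anti-embolic stockings and injections of LMWH, and patients in the IPC group additionally will receive IPC".

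Section 5.6 (Compliance measure) says of the components that both arms share: "No specific compliance measures are designed for the use of ECS and LMWH injections". For the device, the investigator or the surgeon on duty makes five visits a day. If the patient is in bed, the visitor checks that "the sleeves are applied to his legs and that the pump is functioning". The example sheet (Figure 4) has two rows, one for being in bed and one for IPC being on.

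Section 8 (Statistical analysis plan and sample size calculation) makes the primary analysis intention-to-treat with a two-tailed Fisher's exact test. It adds a per-protocol analysis of the primary endpoint that "excluded patients with gross violations of the protocol" and those who stopped a component of prophylaxis early. It also plans a sensitivity analysis restricted to IPC compliance of 90% or more.

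**The concern.** Everything on the compliance sheet concerns the IPC device. Taken literally, every control lacks this information and would be excluded, which cannot be intended. Taken sensibly, only an IPC patient can be excluded for lacking it, and the list has no counterpart for controls.

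The trial is open-label, the sheet is completed by staff who know the allocation, and the investigator holds the allocation list (section 3.1). Whether an IPC patient stays in the analysis would then depend partly on record-keeping by unblinded staff. A missing sheet says nothing about whether the blinded duplex scan was done, so valid primary-endpoint data could be discarded in one arm while similar controls remain. If the discarded patients have a higher risk of thrombosis than the rest, the comparison shifts towards IPC. If they have a lower risk, it shifts the other way.

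**Working it through.** **1. Is the rule one-sided?** Section 3 gives IPC to one arm, section 5.6 records compliance for IPC only, and section 3.4 excludes for absence of that record. No sentence states that controls have no sheet. That is an inference, but nothing on the sheet could apply to them. The one-sidedness belongs to this item. Missed scans, refused autopsy and consent violations can occur in either arm.

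**2. Which analysis does it reach?** Section 8 puts gross violations in the per-protocol analysis, which suggests that set. Section 3.4 says only the final analysis, and the sample size in section 8 allows 10% for protocol deviations, patient decisions and incomplete data. The text leaves the question open.

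**3. Who leaves a blank sheet?** By Figure 4:
- Day Z: in bed at five visits with IPC on at two scores 2/5 = 40%. A patient found in bed who never started IPC would score 0%, which is information.
- Day Y: visits out of bed are entered as a dash, so the sheet is not empty.
- A patient who dies or stops within one or two days still has about 5 to 10 entries at five visits a day.

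The rule should therefore mainly catch lost or unfilled sheets.

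**4. The plan's own figure.** Inputs from section 8: 30% v 12%, two-sided 0.05, power 80%. The usual two-proportion formula gives 80 per arm, and 90 with continuity correction, so 180 in total as stated. Exact Fisher power at 90 per arm is 81.2%. Then 180/0.9 = 200, doubled to 400, or 200 per arm.

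**5. Size of a possible bias.** The documents give no frequency of blank sheets and no event rate in these patients, so both are assumed. Suppose no true effect, with 30% in each full arm of 200. Let a share m of the IPC arm have blank sheets at twice the risk r of the rest:

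(1 − m) × r + m × 2r = 0.30, so r = 0.30/(1 + m).

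Rejection is by full enumeration of the two-tailed Fisher test at 0.05, with 200 controls at 30% against the IPC patients kept at r.

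| m | IPC patients kept | r | Apparent RR | Rejection |
|---|---|---|---|---|
| 0 | 200 | 30.0% | 1.00 | 3.9% |
| 2% | 196 | 29.4% | 0.98 | 4.5% |
| 5% | 190 | 28.6% | 0.95 | 5.5% |
| 10% | 180 | 27.3% | 0.91 | 8.1% |

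At m = 10%, 7.7 of the 8.1 points favour IPC, against 2.0 points with everyone kept.

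**6. Two controls on that result.** If blank-sheet patients have the same risk as the rest, the RR stays at 1.00, and rejection is 4.4% at both 200 v 190 and 200 v 180. The step from 3.9% to 4.4% therefore comes from the unequal group sizes in a discrete test, not from bias. Power at 30% v 12% is 99.3% at 200 v 200 and 99.1% at 200 v 180, so lost power is not the issue.

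**The case against.** The strongest reply has four parts.

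- **The primary analysis is intention-to-treat**, and section 8 places gross violations in the per-protocol set, so the primary result is probably untouched. This is plausible, but section 3.4 does not say so. If it does mean the primary comparison, the conflict with section 8 covers the whole list and this item is one instance of it.
- **A lost sheet is a clerical failure.** If it is unrelated to outcome, the expected bias is nil. This stands. The harm depends on a risk difference that nobody can read from the documents.
- **The larger illustration is generous to the concern.** Ten per cent of IPC patients without sheets would use up that arm's whole allowance for deviations, patient decisions and incomplete data. This stands too, which is why 2% and 5% are shown beside it.
- **An add-on trial's per-protocol set is one-sided by nature.** Section 8 already removes patients who stop IPC, and only one arm can do that. Leaving out patients whose adherence cannot be verified is a defensible convention there. This also stands, and it limits what should be asked of the per-protocol set.

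A reader might infer something stronger: that the rule strips non-starters and early failures from the IPC arm. Suppose 10% of that arm never started and kept the 30% risk while the rest had 12%. The full-arm risk would be 0.9 × 12% + 0.1 × 30% = 13.8%, an RR of 0.46, and dropping the non-starters would give 0.40. The documents do not support charging that contrast to this rule. Under section 5.6 a non-starter found in bed scores 0% and is not missing. In the per-protocol set such patients would very probably leave anyway, as not having followed trial procedures (section 3.4).

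**Conclusion.** The point holds as a one-sided exclusion rule whose population is not named. It follows from sections 3, 3.4 and 5.6 that only IPC patients can be removed for a missing compliance record, and that this removal would contradict section 8 if applied to the primary analysis. The documents do not show that the primary result will be biased. That would need both that section 3.4 reaches the intention-to-treat comparison and that blank-sheet patients differ in risk.

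Under the assumed doubling of risk, the false-positive rate is 4.5% to 5.5% if 2% to 5% of the IPC arm is lost. It reaches 8.1% only at 10%. With equal risk there is no bias. If the rule is confined to the per-protocol set, these figures describe a supportive analysis only. The change is still worth making: it costs very little and removes a filter on one arm that unblinded staff control.

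**What to change.** - Remove the missing-compliance item from the section 3.4 list of exclusions from the final analysis.
- State that a patient without a compliance sheet stays in the intention-to-treat efficacy and safety comparisons. The patient counts as missing only for the compliance endpoint (section 3.5) and the 90%-compliance sensitivity analysis (section 8).
- In the per-protocol set, exclude for documented discontinuation of a component, as section 8 already provides, and not for a missing sheet alone. If the sponsor prefers to exclude unknown compliance there, report how many patients were removed and the result with and without them.

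The cost is one deleted list item and a few sentences. The planned 180, 200 and 400 do not change. The downside is that a few patients of unknown compliance may slightly dilute the per-protocol estimate.

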### **3.5. Endpoints and definitions**

**Primary endpoint:** asymptomatic venous thrombosis of the lower limbs detected by DUS during inpatient treatment.

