## 1. Background

Venous thromboembolism (VTE), including deep vein thrombosis (DVT), superficial vein thrombosis (SVT), and pulmonary embolism (PE), has been considered an important medical-social problem for decades. According to well-known epidemiological data, the VTE incidence in the general population is estimated as 1.0–1.9 cases per 1000 population per year, which can be further classified as 0.5–0.7 cases of pulmonary embolism and 0.5–1.2 cases of deep vein thrombosis. The official data of the Statistical Service of the Russian Federation exceed the average world figures and demonstrate the incidence of venous thrombosis at the level of 1.5–1.6 cases per 1000 population per year. It is well known that one of the important risk factors for VTE development is the recent inpatient treatment, especially accompanied by major surgery. Therefore, stratification of the hospitalized patients according to their individual VTE risk and providing adequate preventive measures are crucial during inpatient treatment. Early ambulation, elastic compression stockings, prophylactic anticoagulation, active blood drainage, and a combination of these methods significantly reduce the risk of postoperative VTE, especially fatal pulmonary embolism, in most surgical patients.

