These and other unresolved issues formed the basis of this study. The main hypothesis of the study was that the combination of IPC with standard preventive measures (above knee anti-embolic elastic compression stockings [ECS] and standard doses of low-molecular-weight heparin [LMWH]) would reduce the incidence of postoperative VTE in patients at extremely high risk (Caprini score of 11 or more). Also, to improve the compliance with IPC, we decided to find out if providing a 6-h free-of-compression night interval (from midnight to 6 am) with the preservation of 18 h of target duration for device application will result in better compliance combined with good clinical outcomes.

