## 2. Rationale and objectives

**The rationale for the Study.** There are no randomized controlled trials examining the effect of the adjunct use of IPC with pharmacologic prophylaxis compared to pharmacologic prophylaxis (LMWH) alone in patients at extremely-high-risk (Caprini score of 11 and more) for VTE prevention.

**Use of Trial Results.** This trial expects to have significant patient safety implications. If the combined use of IPC with pharmacologic prophylaxis proves to be effective, this would change the standard of practice of thromboprophylaxis and will be a major advancement in patient safety.

**Study objectives:** To assess the superiority of IPC at the top of standard prophylaxis with LMWH and ECS compared to standard prophylaxis on postoperative asymptomatic venous thrombosis of lower limbs during inpatient treatment.

[figure not shown]

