### **Secondary objectives:**

- To study the effect of IPC on the asymptomatic venous thrombosis occurrence during inpatient treatment in prespecified groups of patients:
  - Surgical profile,
  - Type of surgery,
  - The urgency of surgery,
  - The radicalism of surgery,
  - Type of anesthesia,
  - Malignant or benign disorder;
  - Preoperative, postoperative or delayed start of LMWH injections,
  - Pre-operative or post-operative IPC application,
- To study the effect of IPC on the isolated calf muscle DVT occurrence during inpatient treatment;
- To study the effect of IPC on the proximal DVT occurrence during inpatient treatment;
- To study the effect of IPC on the symptomatic PE occurrence during inpatient treatment;
- To study the effect of IPC on the fatal PE occurrence during inpatient treatment,

- To study the effect of IPC on the total VTE events that occur during inpatient treatment,
- To study the effect of IPC on the leg skin injury occurrence during inpatient treatment;
- To study the effect of IPC on the major and clinically relevant non-major bleeding occurrence during inpatient treatment;
- To study the compliance with IPC applied in the suggested regimen-required night free-of-compression interval;
- To study the effect of IPC on the symptomatic and asymptomatic venous thrombosis of lower limbs, symptomatic pulmonary embolism occurrence, and VTE related and VTE-non-related mortality during outpatient treatment and rehabilitation 30 and 180 days after surgery.

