#### **Secondary endpoints:**

During inpatient treatment: isolated calf muscle DVT; proximal DVT; symptomatic PE; fatal PE; total VTE events; postoperative mortality; leg skin injury; combination of major and clinically, relevant non-major bleeding; and compliance with IPC.

At 30 days after surgery:

- Combination of symptomatic, asymptomatic venous thrombosis of the lower, limbs and symptomatic PE;
- VTE-related mortality;
- Non-VTE-related mortality.

At 180 days after surgery:

- Combination of symptomatic, asymptomatic venous thrombosis of the lower limbs, and symptomatic PE;
- VTE-related mortality;
- Non-VTE-related mortality.

Following DUS, distal DVT is defined as incompressibility of the affected calf vein, re-occlusion of the previously affected calf vein in case of personal DVT history. Proximal DVT is defined as incompressibility of the affected popliteal and thigh veins, re-occlusion of previously affected popliteal and thigh veins in case of personal DVT history, no blood flow with color flow imaging. Superficial vein thrombosis is defined as incompressibility of the affected superficial vein (GSV and its branches and SSV and its branches). Isolated calf muscle DVT is defined as occlusion of any calf veins except PTV, ATV, and PeV (sural veins, soleal veins). Proximal DVT is defined as occlusion of popliteal and all further cranial venous segments up to the iliac veins (PV, FV, CFV, external iliac vein, common iliac vein). Pulmonary embolism will be suspected according to the classical clinical symptoms and verified with SPECT/CT or CTPA by specific defects of contrast.

Major bleeding is defined by the ISTH criteria as: fatal bleeding; bleeding that is symptomatic and occurs in a critical area or organ; extra-surgical site bleeding causing a fall in hemoglobin level of  $\geq 20$  g/L, or leading to transfusion of  $\geq 2$  units of whole blood or RDC, with temporal association within 24–48 h to the bleeding; surgical site bleeding that requires a second intervention; or surgical site bleeding that is unexpected and prolonged or sufficiently large to cause hemodynamic instability, as assessed by the surgeon.

Clinically relevant non-major (CRNM) is defined as any other bleeding, that does not match the criteria of major but needs some specific measures for hemostasis and/or interruption or preliminary abortion of anticoagulation.

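### The primary endpoint counts only asymptomatic leg thrombosis, so a patient whose only event is a blinded-confirmed symptomatic thrombosis is event-free in the primary test

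*Combined protocol and SAP*

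**What the plan says.** - **Hypothesis (section 1).** Adding IPC to standard prophylaxis "would reduce the incidence of postoperative VTE in patients at extremely high risk". The same section describes the disease broadly: "Venous thromboembolism (VTE), including deep vein thrombosis (DVT), superficial vein thrombosis (SVT), and pulmonary embolism (PE").
- **Objective (section 2).** Superiority of IPC on "postoperative asymptomatic venous thrombosis of lower limbs during inpatient treatment".
- **Primary endpoint (section 3.5).** "asymptomatic venous thrombosis of the lower limbs detected by DUS during inpatient treatment".
- **Inpatient secondary endpoints (section 3.5).** "During inpatient treatment: isolated calf muscle DVT; proximal DVT; symptomatic PE; fatal PE; total VTE events; postoperative mortality", followed by safety and compliance items. None of the DVT or total-VTE items has a symptom qualifier. The day 30 and day 180 composites name symptomatic and asymptomatic leg thrombosis as separate components.
- **Blinding (section 3).** "open-label clinical trial with a blinded assessor for efficacy outcomes".
- **Detection (section 5.4).** Duplex ultrasound (DUS) every 3–5 days, plus an emergency scan on clinical suspicion of DVT or SVT. A blinded expert must verify scan conclusions reached by other staff.
- **Withdrawal (section 3.3).** Any VTE that is a primary or secondary endpoint is a withdrawal criterion.
- **Analysis (section 8).** The primary endpoint is compared by intention-to-treat (ITT) with a two-tailed Fisher's exact test. Cox models of the same endpoint are censored at VTE registration, death or discharge. The 30% control rate is stated for asymptomatic thrombosis.

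**The concern.** There are two separate issues.

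**The exclusion.** The word asymptomatic is restrictive. Section 3.5 itself treats symptomatic and asymptomatic thrombosis as different things in the later composites, and section 8 adds no rule that brings symptomatic leg thrombosis into the primary test. Section 5.4 foresees such events and has them confirmed by a blinded expert. A patient who has one meets a withdrawal criterion and may have no later scan, yet is scored as free of the primary event. The clinically apparent failures of prophylaxis are thus counted as successes in the comparison meant to test whether IPC prevents postoperative VTE. The Cox wording does not say whether such a thrombosis is an event or a censoring.

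**The undefined label.** Thrombosis is defined in section 3.5 by DUS findings only. Nothing says what makes a thrombosis asymptomatic, who decides it, or when. Clinical suspicion arises in open-label care, so the label could be applied differently in the two arms, and it decides which confirmed thromboses enter the primary count.

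**Working it through.** **1. The plan's own figure.** Section 8 gives a 30% control rate and a 60% relative reduction, so the IPC rate is 0.30 × (1 − 0.60) = 12%, a difference of 18 points. With 80% power and two-sided alpha 0.05, the continuity-corrected two-proportion formula gives 90 per arm (80 without the correction). Exact Fisher power at 90 per arm is 81.2%. Allowing for 10% loss, 180 / 0.90 = 200; doubled, this is 400, or 200 per arm randomised and 180 per arm after loss. The figure reproduces. Since the 30% is itself an asymptomatic rate, the sample size matches the endpoint as worded. Exact power for 30% v 12% is 98.6% at 180 per arm and 99.3% at 200.

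**2. Patients with confirmed thrombosis scored as event-free.** Assume a share s of all leg thromboses is symptomatic, equal in both arms, and keep 30% and 12% as the asymptomatic rates. The total rate is p / (1 − s), so the number left out per 200 is 200 × [p / (1 − s) − p].

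| s (assumed) | Control, per 200 | IPC, per 200 |
|---|---|---|
| 5% | 3.2 | 1.3 |
| 10% | 6.7 | 2.7 |
| 20% | 15.0 | 6.0 |

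With equal shares the relative reduction is unchanged. This shows how many patients are misclassified, not a bias.

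**3. Unequal labelling.** Assume no IPC effect and 30% thrombosis in both arms, with shares s₁ and s₂ labelled symptomatic. The counted rates are 0.30 × (1 − s₁) and 0.30 × (1 − s₂). The rejection rate is the sum, over all pairs of counts, of the product of the two binomial probabilities wherever two-sided Fisher p ≤ 0.05.

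| Labelled symptomatic (assumed) | Counted rates | Type I error, 180 per arm | Type I error, 200 per arm |
|---|---|---|---|
| 10% v 10% | 27.0% v 27.0% | 3.8% | 3.9% |
| 2% v 5% | 29.4% v 28.5% | 4.1% | 4.3% |
| 10% v 15% | 27.0% v 25.5% | 4.8% | 5.0% |
| 2% v 10% | 29.4% v 27.0% | 6.3% | 6.8% |
| 10% v 20% | 27.0% v 24.0% | 8.0% | 8.6% |
| 10% v 30% | 27.0% v 21.0% | 22.7% | 25.2% |

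With 10% in one arm, 5% is first exceeded at 16% in the other arm for 180 per arm (5.2%) and at 15.5% for 200 per arm (5.2%), a gap of about 6 points. Starting from equal counts, 18 of 54 thromboses in one arm (180 per arm; 54 v 36, p = 0.038) or 19 of 60 (200 per arm; 60 v 41, p = 0.038) would have to be relabelled, with none in the other arm, to reach p < 0.05.

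**4. What the secondary endpoints recover.** Proximal DVT and isolated calf muscle DVT count a thrombosis whether or not it had symptoms, but "Isolated calf muscle DVT is defined as occlusion of any calf veins except PTV, ATV, and PeV". A symptomatic tibial or peroneal DVT, or a symptomatic SVT, therefore fits neither. It can count in total VTE events, whose components section 3.5 does not list, though the general description of VTE in section 1 would cover it.

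**5. Power with all confirmed thromboses counted.** Rates become 0.30 / (1 − s) and 0.12 / (1 − s). For s = 5%, 10% and 20% these are 31.6% v 12.6%, 33.3% v 13.3% and 37.5% v 15.0%. Exact Fisher power at 180 per arm is 99.1%, 99.4% and 99.8%.

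**The case against.** The asymptomatic endpoint is a deliberate choice, stated consistently in the objective, the endpoint and the sample size, and a narrower screening endpoint under a broader hypothesis is a surrogate, not a contradiction. That stands as far as consistency goes. It does not change the result that a thrombosis the trial itself has confirmed, blind, is scored as absent.

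The secondary objective "To study the effect of IPC on the total VTE events that occur during inpatient treatment" has its own endpoint, tested with Fisher's test, so most of the unrestricted comparison will be reported. This also stands. A reader might infer that symptomatic thromboses are lost to the trial; they are not. They are missing only from the primary test.

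A reader might also infer that unblinded staff assign the symptom label, and so that the primary result is biased. The documents do not say so. Section 3 promises a blinded assessor for efficacy outcomes, sections 3.1 and 5.4 place scanning and verification with blinded experts, and on the label itself the plan is silent. The two detection routes in section 5.4 even suggest a workable distinction. What remains is that suspicion arises in open-label care and no rule governs its use.

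Finally, every labelling share above is assumed, and the large error rates need a large imbalance that nothing in the documents suggests. This is accepted.

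**Conclusion.** The concern holds in this form. The restrictive word in section 3.5 makes a patient whose only event is a blinded-confirmed symptomatic leg thrombosis event-free in the primary ITT Fisher test. It is tempting to attribute this to the missing definition, but a perfectly defined label would exclude the same patients. The missing definition and missing assessor are a second, separate weakness.

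Size: if 5–20% of thromboses are symptomatic, about 3 to 15 control and 1 to 6 IPC patients per 200 are misclassified. Type I error passes 5% only when labelling differs by about 6 points or more from a 10% base; an assumed 10% v 15% stays at or below 5%. The size and direction of any real imbalance are unknown. These figures rest on assumed shares, the section 8 rates and independent binomial counts. No sample-size or power error is claimed. The point should be corrected because the change is cheap and brings the primary test closer to the hypothesis.

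**What to change.** In sections 2, 3.5 and 8:

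- Define the primary endpoint as any new lower-limb venous thrombosis during inpatient treatment, symptomatic or not, confirmed by the blinded DUS expert.
- Count that same occurrence as the event, not as a censoring, in the Cox models.
- Report the asymptomatic-only endpoint as secondary, labelled by detection route: found on a scheduled scan with no suspicion recorded before it, or found on a suspicion-triggered scan.
- Add a sensitivity analysis limited to the calf and thigh veins, which section 5.3 requires at every scan.

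Keeping the asymptomatic endpoint as primary with only a labelling rule would clarify the plan but not cure the problem: the exclusion would remain, and suspicion would still be recorded in open-label care.

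**Cost.** Wording in three sections, one case report form field for suspicion recorded before each scan, and one sensitivity analysis. No extra scans or patients. The 30% planning rate becomes slightly conservative.

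**Downside.** Some primary events would come from scans triggered by open-label suspicion. Both arms are scanned every 3–5 days, so the next scheduled scan would probably find most of these anyway. Iliac thromboses are the exception, because section 5.3 has the iliac veins examined only on clinical suspicion; the calf-and-thigh analysis addresses that part.
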